## 15.4 APPENDIX 4: ADHER2 DC VACCINE MANUFACTURING SCHEMA

### Description of AdHER2 DC Vaccine Manufacture

**Day 0** Prior to the scheduled administration of the Dendritic Cells vaccine, one cryopreserved monocytes enriched aliquot will be thawed, washed and evaluated for cell count and viability. Monocytes will be resuspended in media containing 90% RPMI-1640, 10% auto HF plasma or allo HIF AB plasma, 2000 IU/mL IL-4 2000 IU/mL rGM-CSF and 10 mcg/mL gentamicin.

**Day 1** No processing required

**Day 2** Fresh media and cytokines (2000 IU/mL rIL-4, 2000 IU/mL of rGM-CSF) will be added to the culture; KLH will be added at a final concentration 10 mcg/mL.

**Day 3** The AdHER2 vector will be added at a ratio of 3000 viral particles per monocytes plated on Day 0; vector viral particles will be added at -24 hrs from harvesting.

Vector transfection will occur over 4 hours before the addition of maturation cocktail at -20 hrs from harvesting. Maturation cocktail consist of LPS and IFN- $\gamma$  at a final concentration of 30 ng/mL and 1000 IU/mL, respectively.

Removal of sample for -24 hours sterility testing.

**Day 4** Final harvest, packaging and lot release testing of autologous AdHER2 DC vaccine preparation. The final transfected, volume-reduced mature AdHER2 DC vaccine product will be prepared in sterile syringes for fresh administration intradermally.

The AdHER2 DC vaccine product will be prepared as summarized above using a comprehensive, validated manufacturing process described in the DTM Standard Operating Procedures (SOP). Detailed SOP for processing, labeling, storage, and quality assays are also available on site in the Cell Processing Section of DTM. All DTM SOPs related to the manufacture of the AdHER2 DC vaccine will be included in the Sponsor-Investigator held IND to be submitted for the product.

### **Vaccine Processing Steps and In Process Testing**

Multiple sample and assay timelines for the manufacturing processes of the AdHER2 DC vaccine are detailed in the CMC file in DTM and include:

- Timeline for processing and in process testing of autologous mononuclear cells to generate monocyte and lymphocyte fractions via elutriation for cryopreservation.
- Timeline for processing and in process testing during AdHER2 DC vaccine manufacture.

### **Vaccine Manufacture Critical Reagents**

Critical reagents in the manufacture of autologous AdHER2 DC vaccine include interleukin-4 (IL-4), KLH (Keyhole Limpet Hemocyanin), sagramostim (GM-CSF) and reference endotoxin (E. coli). **Detailed information on these agents is outlined in protocol Section 13,**

**Pharmaceutical Information.** Letters of Authorization to cross-reference the master files of these agents will be included with the formal IND submission for the product.

### **Vaccine Release Testing**

Release testing will include not only safety testing (microbiological testing) but will also include any product characterization that is being done such as identity, purity, and potency testing. The following tests will be performed related to AdHER2 DC vaccine release criteria and quality control:

#### **a) Vaccine Product Safety Testing**

1. Sterility (bacterial and fungal) testing of all in-process and final product samples of the AdHER2 DC vaccine product will be done by the Bactec automated blood culture system. *Although final product sterility testing will be performed, results will not be available as a release criterion.*

DTM has completed and published the results of a study demonstrating that both the BacT/Alert (BioMerieux) and the Bactec (Becton Dickinson) automated culture systems are superior to the CFR/USP method for sterility testing of cell therapy products (seeded

study; *Khuu HM et al. Cytotherapy 2004; 6(3): 183-195*). They also published a parallel testing study of CFR/USP vs. Bactec, for sterility testing of actual cell therapy products from their facility. Results of the parallel studies show that the automated culture methods had fewer false positives than CFR/USP (*Khuu HM et al. Transfusion 2006; 46: 2071-82*). Based on the analysis of both studies, DTM has sufficient data to implement the Bactec system as the replacement for the CFR/USP method.

Justification for use of automated system in place of CFR/USP method is based on the results of the studies described above. In the seeded study, 10 different organisms were seeded into mononuclear cell products suspended in 6 different media, one of which was X-Vivo20 (which contains gentamicin), and one of which was our standard freeze mix (Plasmalyte A, human serum albumin, Pentastarch, DMSO, Dornase, and heparin), which is used to cryopreserve all products in this protocol. The antibiotic level tested in the seeded study is **50mg/mL** and this level was shown to be non-inhibitory in the automated culture system. This is the same level in the samples for sterility for the product in this IND.

2. Negative gram stain must be documented
3. Sterility of -24hrs in process sample must be documented
4. Mycoplasma testing will be done by Mycoplasma PCR method (Roche) but results will not be available for use as a release criterion
5. Endotoxin testing will be done by the KQCL method; endotoxin level must be < 5EU/ml.
6. Transfusion-transmitted disease (TTD) testing will be performed using methods described in our Master File CC-MF-11054 (Attachment 8-A), with the following modification. Testing is performed by Blood Systems Laboratories in Tempe, AZ CLIA Reg #03D0911463). Agents include *T. cruzi* as well as those listed. Syphilis is tested using PK-TP assay, instead of RPR.

**b) Vaccine Product Characterization**

1. Total cell number as determined using an automatic counter.
2. Viability using Trypan blue dye exclusion with a minimum viability of  $\geq 60\%$  as release criteria.
3. Cell phenotype and expression for HER2neu by FACS.  
Phenotype markers will include: **CD14, CD38, CD54, CD83, CD86, CD 340 (HER2neu), CCR7, HLA-DR**. **Key phenotype markers in bold.**
4. Day 3 in process DC supernatants prior to transfection with adenovirus for cytokine assessments by multiplex and proteomic array (for research purposes).

**Vaccine Product Release and Action Plans for Positive Results on Safety Testing**

General action plans for dealing with positive tests for sterility, mycoplasma, and endotoxin testing are presented in our Master File BB-MF-11054 (Attachments 9-B through 9-D). As noted above, not all safety testing will be available prior to release of the AdHER2 DC vaccine product. For testing with final results available, results must be within pre-specified limits and documented on the Certificate of Analysis before the product is released for administration to the patient.

### **Vaccine Final Product Preparation Steps (fresh infusion)**

The final AdHER2 DC vaccine product will be harvested from the 5-day culture product and packaged for fresh infusion on the same day.

### **Vaccine Product Tracking and Labeling**

The system for labeling and tracking of all products in this IND will be the same as the general system used in the DTM Cell Processing Facility, described in their Master File BB-MF-11054, section XI.

### **Vaccine Product Administration**

Autologous AdHER2 DC vaccines will be harvested from the 5-day culture product as previously described and packaged for fresh administration on the same day according to DTM Standard Operating Procedures. The protocol specified AdHER2 DC vaccine dose of  $5 \times 10^6$  viable cells,  $10 \times 10^6$  viable cells,  $20 \times 10^6$  viable cells or  $40 \times 10^6$  viable cells will be concentrated in a final total volume of 1.0mL for intradermal administration immediately upon receipt in the clinical setting. Post packaging testing of DC vaccines produced by DTM indicates that the product should be stable for at least 2 hours.

Patients will have vital signs monitored for one hour following administration of the first dose of AdHER2 DC vaccine and for 15 minutes with all subsequent doses if there are no significant acute adverse systemic clinical events (e.g. fever, hypotension, wheezing, rash/urticaria) documented after the first dose. It is anticipated that the primary adverse events associated with AdHER2 DC vaccination will be local injection site reactions, and possibly symptoms related to local anti-tumor inflammatory responses at sites of primary and metastatic disease including focal organ discomfort and/or reactive pleural and peritoneal effusions.

## 15.5 APPENDIX 5: ADHER2 DENTRITIC CELL VACCINE REPORT CARD

[figure not shown]
Date/Time Vaccine Administered: \_\_\_\_\_ Administered By: \_\_\_\_\_

Study  Part I  Part II      Vaccine Dose  10e cells  20e cells  40e cells

Study Week \_\_\_\_\_      Vaccine Dose #  1  2  3  4  5

	Injection Site: Forearm	Injection Volume (mL)	ID Wheal Present?	DA Y 1	DA Y 2	DA Y 3	DA Y 4	DA Y 5	Date resolved
Site #1	 Left  Right		 Present  Absent	 0  1  2  3	 0  1  2  3	 0  1  2  3	 0  1  2  3	 0  1  2  3	
Site #2	 Left  Right		 Present  Absent	 0  1  2  3	 0  1  2  3	 0  1  2  3	 0  1  2  3	 0  1  2  3	
Site #3	 Left  Right		 Present  Absent	 0  1  2  3	 0  1  2  3	 0  1  2  3	 0  1  2  3	 0  1  2  3	
Site #4	 Left  Right		 Present  Absent	 0  1  2  3	 0  1  2  3	 0  1  2  3	 0  1  2  3	 0  1  2  3	

Total Injection Volume: \_\_\_\_\_

### Injection Site Reaction Grading (NCI CTCAE v4.03)

- 0 No Reaction
- 1 Tenderness *with or without* associated warmth, redness, itching.
- 2 Pain, swelling (edema), lipodystrophy (shrunken area of the skin due to loss of fat), or phlebitis (inflammation of veins in the skin).
- 3 Ulceration or necrosis (skin break down); severe tissue damage.  
Operative intervention indicated.
- 4 Life-threatening consequences. Urgent intervention indicated.

Note: If you have a reaction that lasts longer than 5 days please continue to describe it on the back of this page.

Print Name: \_\_\_\_\_

Signature: \_\_\_\_\_

## **15.6 APPENDIX 6ANTI-HER2 ANTIBODY AND CELLULAR RESPONSES**

The majority of the testing on this study will be done in the NIH Clinical Center clinical laboratory following their guidelines for blood collection and tube type. The appropriate tube for uncommon laboratory tests and immunologic research specimens and where they should be sent are as follows:

### **Quantitative Anti-HER2 Antibody Testing: Weeks 0, 8, 16, 24, 32, 40, 48, 60, 76, 100, and 124**

**Purpose:** To determine the immunogenicity of autologous Ad HER2 dendritic cell vaccination as measured by a 3-fold increase in anti-HER2/neu antibody concentration (measured as mcg/mL) or a 4-fold increase in antibody dilution titers over baseline.

**Specimen Processing:** 1 10mL Red Top Clot activator

Specimens will be processed by the Clinical Support Laboratory Leidos Biomedical Research, Inc. Serum will be aliquoted into vials and cryopreserved until ready for interrogation in batched specimen assays.

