#### 1.2.1.1 Trastuzumab (Herceptin®)

Trastuzumab (Herceptin®) is a recombinant humanized mouse monoclonal antibody (MAb) that binds to the extracellular (EC) domain of the HER2 receptor and was approved by the FDA in September 1998. It is approved for the adjuvant treatment of early-stage breast cancer with nodal spread (or without nodal spread if the tumor is high risk) as well as for first and second-line/salvage therapy for metastatic breast cancer. In the adjuvant setting trastuzumab is used in several ways:

- As part of a treatment course including chemotherapy with doxorubicin, cyclophosphamide and either paclitaxel or docetaxel, known as “ACTH”.
- With chemotherapy drugs docetaxel and carboplatin in a regimen known as “TCH”.
- Alone after treatment with multiple other therapies, including anthracycline-based therapy.

Trastuzumab has two approved uses in metastatic breast cancer:

- As first line treatment in combination with paclitaxel.
- As a single agent in patients who have received one or more courses of chemotherapy for metastatic disease.

Therapy typically involves an initial trastuzumab dose of 4mg/kg IV followed by 2mg/kg IV administered weekly for 52 weeks, alone (salvage therapy) or in combination with paclitaxel for the first 12 weeks (adjuvant and first-line therapy). However, clinical efficacy is limited to patients with 3+ HER2 tumor expression documented by immunohistochemistry (IHC) or gene amplification by fluorescent *in situ* hybridization (FISH). IHC is a subjective measurement of HER2/neu protein while FISH is an objective measurement of amplification of the HER2 oncogene. Despite the high level efficacy in combination with chemotherapy, the overall response rate of women diagnosed with HER2-positive metastatic breast cancer and treated with trastuzumab as a single first-line agent is only 26% clearly indicating there is room for improvement in therapeutic options. In addition, a significant number of patients are unresponsive to trastuzumab and most eventually experience clinical progression while on therapy, presumably due to trastuzumab resistance, whose mechanism is poorly understood.

Trastuzumab is also approved for use in combination with cisplatin and either capecitabine or 5-fluorouracil in treatment naïve patients with HER2-positive metastatic stomach cancer or cancer of the gastroesophageal junction.

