#### 1.2.9 Previous Human Experience with an Extracellular/Transmembrane/Intracellular HER2/neu Vaccine

Our collaborator [name], and his colleagues at the Karolinska Institute in Sweden have conducted a pilot clinical trial of a plasmid DNA human HER2/neu vaccine encoding the extracellular (EC), transmembrane (TM) and mutated intracellular (ICmutated) domains (ECTMICmutated) given with GM-CSF and IL-2. As a safety measure, a two base pair mutation was introduced in the IC domain to remove an autophosphorylation site that confers oncogenicity and maximize safety. The vaccine was administered to a total of eight patients and no clinical issues of acute toxicity, autoimmunity or cardio toxicity were identified. As might be expected with a DNA plasmid construct, the vaccine demonstrated limited immunogenicity: no specific T-cell proliferation following *in vitro* stimulation of *ex vivo* PBMCs with recombinant human HER2 protein was induced by vaccination. In fact, immediately following three complete cycles of vaccination, no or even decreased HER2-specific CD4+ T-cell responses were observed, but a significant increase in MHC class II restricted HER2-T-cell responses was detected at long term follow-up. Because concurrent trastuzumab therapy was permitted during the study,  $\lambda$ -subclass specific ELISAs were performed to measure endogenous antibody production without trastuzumab interference. Importantly, in a subgroup of patients, HER2-pDNA vaccination induced and boosted HER2-specific antibodies that could be detected for several years following the last vaccine administration.

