## 2.1.3 Part II Eligibility

2.1.3.1 Malignant soft tissue and bone tumors and recurrent or progressive, metastatic solid tumors who have progressed on standard therapies.

2.1.3.2 Recurrent or progressive metastatic disease after standard of care HER2-targeted therapies; i.e. trastuzumab (HerceptinTM), pertuzumab (PerjetaTM), lapatinib (TykerbTM), ado-trastuzumab emtansine (TDM1) (KadcylaTM) or other HER2-directed therapies.

2.1.3.3 Stable, concurrent use of tamoxifen or aromatase inhibitors for hormone receptor positive breast cancer is permitted.

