## **3 STUDY IMPLEMENTATION**

### **3.1 STUDY SCHEMA AND DESIGN**

This is an open label, single site, non-randomized, two-part, phase I study of an autologous dendritic cell (DC) vaccine transduced with AdHER2 to determine vaccine safety, immunogenicity and preliminary activity. The study design schema is outlined in [Figure 11](#).

Once enrollment eligibility is confirmed and informed consent is obtained, the patient will be scheduled for an apheresis of up to 18 liters to collect mononuclear cells by counter-flow elutriation, aliquoted into minimum of 6 vials with up to  $333 \times 10^6$  cells/vial that will be cryopreserved for future preparation of the autologous AdHER2 DC vaccine product. If the collected apheresis products are not adequate for 5 doses of vaccine, the patient may undergo

additional apheresis per investigator's discretion. Co-enrollment in the Indium trastuzumab imaging protocol 07-C-0101 will be offered to those patients that are interested and eligible.

Note: In order to be cleared for the next treatment, a safety visit (i.e., physical and clinical laboratory assessments, review of toxicities/adverse events) must occur within 7 days prior to the treatment. Treatment visits can also be safety visits for previous injections. This is so the treating physician will evaluate the patient for toxicities potentially caused by previous injections.

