## **4 CONCOMITANT MEDICATIONS/MEASURES**

- Patients are allowed to be on concomitant therapy with tamoxifen or aromatase inhibitors for ER+ tumor status.
- Patients may be on concomitant drugs to prevent skeletal related events (SRE), including bisphosphonates and denosumab.
- Study subjects will be allowed to take multivitamins, analgesics (NSAIDS or acetaminophen), antipyretics, and antihistamines for symptomatic relief of local or systemic injection site reactions.
- Patients are allowed to continue on medications as clinically indicated for treatment of chronic medical conditions e.g. hypertension, diabetes, hypercholesterolemia, etc.
- Excluded Therapy:
  - Trastuzumab, pertuzumab, lapatinib, ado-trastuzumab emtansine (TDM1) or other HER2-directed therapies *within 1 week* of study enrollment.
  - Chemotherapy: Concomitant use of chemotherapy is not allowed during this trial.
  - Anti-Cancer Radionuclides: Concomitant use of anti-cancer radionuclides is not allowed during this trial. Patients will be allowed to co-enroll in studies of novel radionuclide imaging agents e.g. Indium CHX-A DTPA trastuzumab.
  - Secondary Hormonal Therapies: Concomitant use of supplementary hormonal treatments other than tamoxifen or aromatase inhibitors is not allowed.
  - Corticosteroids: Concomitant, chronic systemic corticosteroids are not allowed during this trial (excepting emergent use for clinical indications). However, the use

of inhaled corticosteroids, intranasal sprays and topical creams on limited body areas is allowed.

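### In Part II the antibody-responder rule does not separate residual therapeutic anti-HER2 antibody from the patient's own; if the assay reads the drug, the responder fraction is biased downward.

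*Combined protocol and SAP*

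**What the plan says.** - **Rule.** Appendix 6 (section 15.6) defines immunogenicity as "measured by a 3-fold increase in anti-HER2/neu antibody concentration (measured as mcg/mL) or a 4-fold increase in antibody dilution titers over baseline". Sections 1.1.1, 11 and 11.3 use the same thresholds for both Parts. Section 11.3 reports the fraction with 80% and 95% confidence intervals.
- **Baseline.** The heading in Appendix 6 is "Quantitative Anti-HER2 Antibody Testing: Weeks 0, 8, 16, 24, 32, 40, 48, 60, 76, 100, and 124". The Study Calendar (section 3.4) agrees: its anti-HER2 antibody row has one pre-vaccine sample, at Week 0.
- **Part II patients.** Section 2.1.3 requires "Recurrent or progressive metastatic disease after standard of care HER2-targeted therapies" and lists trastuzumab, pertuzumab, lapatinib and T-DM1. Part I patients are naive to these (section 2.1.2).
- **Washout.** Section 4 excludes these agents "or other HER2-directed therapies *within 1 week* of study enrollment". The limit runs to enrollment, not to Week 0.
- **Shared target.** Section 1.2.1.1 describes trastuzumab as an antibody "that binds to the extracellular (EC) domain of the HER2 receptor"; the vaccine encodes that domain too.
- **Known interference.** Section 1.2.9 says that an earlier HER2 vaccine pilot used light-chain-specific ELISAs to measure the patients' own antibody. The reason given is "Because concurrent trastuzumab therapy was permitted during the study".

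**The concern.** A fold-rise rule works when the baseline reading is the patient's own antibody. In Part II, a patient who recently stopped trastuzumab, pertuzumab or T-DM1 may still carry drug at Week 0. An assay that reads total anti-HER2 antibody would add that drug to the denominator. By the later visits some or all of it would have cleared, so the patient's own response would have to replace the lost drug before any rise showed. True responders could then be scored as non-responders.

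The nearest safeguards do not cover this:

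- Footnotes 8-11 of the Study Calendar drop samples once a new treatment has started. They do not deal with drug stopped before Week 0.
- The peptide arrays and immunoglobulin sub-class work (Appendix 6) and the third-party characterization (Appendix 8) are descriptive. They are not linked to the responder call.

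What is at stake is the Part II estimate for a primary objective, and any comparison with Part I, where prior therapy cannot have this effect. Section 3.1.2 also uses immunogenicity, with clinical outcomes, in choosing the dose for later studies. The planned intervals would not reflect the bias, and more patients would not reduce it.

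**Working it through.** The plan gives no target rate, test or power for immunogenicity, so there is no stated figure to reproduce. The check is algebra, followed by an illustration on assumed inputs.

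**Inputs from the documents:** thresholds of 3 (concentration) and 4 (titer); baseline at Week 0; up to 30 evaluable patients in Part II (section 11.2).

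**Inputs not in the documents, therefore assumed:** the assay adds drug and own antibody together; k = drug divided by own antibody at Week 0; r = share of that drug left at the later visit; no new drug after Week 0.

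**Step 1: the true rise needed.** With own antibody E0 at Week 0 and E1 later, the assay sees

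(E1 + r·k·E0) / (E0 + k·E0).

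Setting this at or above the threshold f gives E1/E0 ≥ f(1 + k) − r·k = f + k(f − r).

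- If the drug is gone (r = 0), the 3-fold rule needs 3 + 3k and the 4-fold rule needs 4 + 4k. At k = 1 these are 6-fold and 8-fold.
- If none has cleared (r = 1), the 3-fold rule at k = 1 still needs 3 + 1 × 2 = 5-fold.
- Since r cannot exceed 1 and f is at least 3, the needed rise is never below f. Under this model, leftover drug cannot create a false responder.

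**Step 2: illustration for the fraction.** Assume a true responder fraction of 50%, a log-normal own-antibody rise with SD 1.0 on the natural-log scale, the 3-fold rule and r = 0. Affected patients are then scored as responders with probability 1 − Φ(ln(1 + k)). The Part II fraction is share × that value + (1 − share) × 50%.

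| k | true rise needed | scored among affected | Part II, 20% affected | Part II, 50% affected |
|---|---|---|---|---|
| 0.25 | 3.75 | 41% | 48% | 46% |
| 0.5 | 4.5 | 34% | 47% | 42% |
| 1 | 6 | 24% | 45% | 37% |
| 2 | 9 | 14% | 43% | 32% |
| 5 | 18 | 4% | 41% | 27% |

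Other assumptions, at k = 1 with half affected: a true 30% reads 21%, a true 70% reads 57%, and a true 50% reads 33% to 41% for an SD of 0.7 to 1.5.

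**Step 3: against the planned precision.** Exact intervals for 15/30 are 37% to 63% (80%) and 31% to 69% (95%). At k = 1 with half affected, about 11 of 30 would be scored: 25% to 50% (80%) and 20% to 56% (95%). These overlap the unbiased intervals. At k = 0.25 with 20% affected the loss is 1.8 points, about half a patient in 30.

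**The case against.** **The assay may already be drug-tolerant.** No available text names its format, and part of section 1.2.10, just before the antibody paragraph in 1.2.10.2, was not available for this review. The authors clearly know of the interference. This objection stands against any claim that the plan lacks such an assay. It does not answer the narrower point: the responder definition and the analysis text require no such readout.

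**Size is not known.** This is correct. The documents give no drug level, clearance or cross-reactivity, and the table shows that the loss can be trivial. Section 1.2.9 concerns concurrent trastuzumab, so it shows that interference can occur, not how much remains after stopping.

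**The gap to Week 0 exceeds one week.** Also correct. Apheresis and cryopreservation (section 3.1) and a five-day culture (Appendix 4) follow enrollment. This lowers k by an unstated amount.

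**Few patients may be affected.** Patients whose last HER2 therapy was lapatinib, which is not an antibody, or whose last antibody was long ago, are unaffected.

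**The consequence is limited.** Section 11 seeks only an approximate estimate. Comparing 6 with 24 patients across the two Part II dose levels is weak with or without this problem.

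A reader might also infer false responders from imaging trastuzumab, since "Patients will be allowed to co-enroll in studies of novel radionuclide imaging agents" and co-enrollment in the "trastuzumab imaging protocol 07-C-0101 will be offered to those patients that are interested and eligible". The documents do not support that. They give neither the mass nor the timing relative to Week 0, and the offer appears alongside the initial apheresis in text common to both Parts.

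**Conclusion.** The point holds in conditional form. As written, the rule counts any anti-HER2 antibody in the Week 0 reading. If the Part II assay reads therapeutic antibody, drug that clears after Week 0 raises the true rise needed from 3 to 3 + 3k and biases the fraction downward in recently treated patients.

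This direction assumes additive signals, no new drug after Week 0 and no masking of own antibody by the drug. Masking at Week 0 would act the other way, and the available text does not allow it to be excluded. The percentages in the table rest wholly on assumed k, share affected, true fraction and spread; they show scale and are not a forecast.

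Two stronger readings are not supported: that the assay is known to be drug-sensitive, and that the Part II fraction will be materially wrong. The issue merits correction because it touches a primary objective and is cheap to settle. It does not undermine the trial, and Part I carries no such residue from prior therapy.

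**What to change.** 1. State in the Part II responder definition that it is scored on a readout the laboratory has confirmed neither detects, nor is masked by, the patient's prior therapeutic anti-HER2 antibody. If the assay already meets this, one sentence saying so is enough.
2. Keep the unrestricted fold-rise as a supportive result.
3. Record the date of the last anti-HER2 antibody dose, naming T-DM1. Section 2.3.2 does not ask explicitly for that date. The Appendix 12 form has a single date-or-duration column and does not name T-DM1, although its agent column is open.
4. Pre-specify a sensitivity analysis of the Part II fraction by time since that dose, or excluding patients with detectable drug at Week 0.

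**Cost.** Possibly another assay on serum already stored for batched testing, a few lines of analysis text, and a date that may need chart extraction. A light-chain-specific readout misses own antibody of the other light chain, and section 1.2.9 supports it only for trastuzumab, so other antibodies need their own check. With at most 30 patients, the subgroups will be small. No change to washout, co-enrollment or treatment is proposed.
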